#### 5.1.3.2 QT Prolongation (Objective 2.3.2.3; Outcome Measures 3.2.3.1, 3.2.3.2, 3.2.3.3)

We will compare the mean change in QTcF from screening to weeks 2, 8, and 13 (3.2.3.1) between Arm 1 and Arm 2 in the safety set using a GEE model with exchangeable correlation structure and time by treatment interaction terms (treating time as a categorical variable).

We will compare the change from baseline in QTcF over time between arms using a linear mixed effects model. Randomization arm and week (time) will be fixed effects and participant ID will be a random effect.

We will compare the odds of participants having maximum occurrence of absolute QTcF  $\geq 480$  ms and  $<500$  ms, or  $\geq 500$  ms (3.2.3.2) between Arm 1 and Arm 2 in the safety set using a proportional odds model, if the proportional odds assumption is satisfied. We will assess the proportional odds assumption using the score test for the proportional odds assumption implemented in SAS PROC LOGISTIC. If the score test indicates a statistically significant result at the 0.05 level, we will also assess the proportional odds assumption graphically to confirm. If graphical evidence suggests the proportional odds model is valid, we will use it for analysis.

If the proportional odds assumption does not hold, we will instead estimate the difference in binomial proportions and 95% confidence intervals for the collapsed category of QTcF  $\geq 480$  ms (including QTcF  $\geq 500$  ms), and separately for the category QTcF  $\geq 500$  ms.

The analysis of outcome measure 3.2.3.3 will follow the same approach as that of 3.2.3.2.

#### 5.1.3.3 Time to stable culture conversion in liquid media, and solid media at week 26 (Objective 2.3.2.4; Outcome Measure 3.2.4)

Time to stable culture conversion in liquid media will follow the same approach as described in Section 5.1.1, except we will censor participants at week 26 instead of week 12.

Time to stable culture conversion in solid media will be analyzed separately, and also follow the same approach as described in Section 5.1.1, except we will censor participants at week 26 instead of week 12.

#### **5.1.3.4 Proportion with culture conversion at week 8 and 12 (Objective 2.3.2.5; Outcome Measure 3.2.5)**

We will compare the proportion of participants with stable culture conversion by week 8 and week 12 between Arm 1 and Arm 2 in the efficacy set. We will analyze liquid and solid cultures separately. We will present the difference in proportions and exact 95% confidence intervals.

#### **5.1.3.5 Proportion with one or more SAE (Outcome Measure 3.2.8)**

We will estimate the proportion of participants with one or more SAEs of any grade between Arm 1 and Arm 2 in the safety set using the same approach as described in Section 5.1.1

As in Section 5.1.1, supplementary analyses will compare SAEs between arms up to week 13 and up to week 26.

#### **5.1.3.6 Time to Positivity (Objective 2.3.2.6, Outcome Measure 3.2.6)**

We will compare time (days) to positivity of TB cultures between Arm 1 and Arm 2 in the efficacy set separately at weeks 1, 2, 3, 4, 6, 8, 10, and 12 using Cox proportional hazards models or log-rank tests. We will present the hazard ratios and 95% confidence intervals for each week.

We will include side-by-side box plots to show the distribution of time to positivity at each visit in each of Arms 1 and 2. In exploratory analyses, we may consider comparing time (days) to positivity of TB cultures between Arm 1 and Arm 2 in the efficacy set using a random effects joint model for time-to-event data with repeated measures. We may also consider other models and mechanistic approaches.

#### **5.1.3.7 Chest X-Ray Scores (Objective 2.3.2.7; Outcome Measure 3.2.7)**

Each participant will have a CXR Score computed at screening and at EOT (week 13 for Arm 1; week 26 for Arm 2). We will compute the difference in scores from baseline to EOT between arms in the efficacy set using linear regression, with adjustment for stratification factors of HIV status and advanced disease status.

We will carry out two analyses for this outcome; (1) based on the site reading of CXR, and (2) based on the central reading of CXR. The central reading will take precedence when presenting results.

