3.2.3 QT interval

We derive the outcome measures defined below from ECG readings, which the site conducts in triplicate (three ECGs 5-10 minutes apart). We will use the mean of all measurements (up to 3) that are readable and available.

3.2.3.1 Mean baseline QTcF and change from baseline in mean QTcF at weeks 2, 8, and end of treatment (EOT) (Arm 1, week 13; Arm 2, week 26)

3.2.3.2 Occurrence of absolute QTcF  $\geq 480$  ms and  $< 500$  ms, and  $\geq 500$  ms, at any time during study treatment

3.2.3.3 Occurrence of QTcF change from baseline of  $\geq 30$  ms and  $< 60$  ms, and  $\geq 60$  ms, at any time during study treatment

3.2.4 Time to stable culture conversion in liquid and solid media through week 65

Defined as the first of two (consecutive or non-consecutive) negative sputum cultures without an intervening positive culture, and/or visits wherein the participant is unable to produce sputum and has no signs of active TB. Conducted separately for liquid and solid media.

3.2.5 Proportion of participants with culture conversion at weeks 8 and 12 across all study arms.

Liquid (MGIT) and solid media analyzed separately.

3.2.6 Time (days) to positivity in liquid culture (MGIT) after start of treatment through week 65

We will report the median (Q1, Q3) times to positivity in liquid culture at each time point (weeks 1, 2, 3, 4, 6, 8, 10, and 12) in Arm 1 and Arm 2.

3.2.7 Change in chest X-ray (CXR) score from baseline to end of treatment (EOT).

Sites conduct the baseline chest X-ray during screening. We will compute the chest X-ray score with the following validated formula (Ralph et al. Thorax 2010):

CXR Score = percent of total lung affected by any pathology + 40 (if cavitation is present).

We will compute the CXR scores based on both site assessment of the chest X-ray and an assessment by independent central reviewers blinded to study treatment.

- 3.2.8 Proportion of participants with one or more serious adverse events (SAEs) through week 65
- 3.2.9 Proportion of participants who have a TB relapse from EOT until week 65  
For participants who had successful culture conversion through the end of study treatment, TB relapse is defined as a recurrence of TB emanating from the same strain as the participant's originally diagnosed TB, which will be determined through molecular genotyping.

- 3.2.10 Proportion of participants who have a TB recurrence from EOT until week 65
- 3.2.11 Plasma pharmacokinetic parameters for CFZ

Arm 1

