### 6.2 Baseline Characteristics

- Summary of age, sex, gender, country, Karnofsky Score (50-70, 80-100), BMI, HIV Status (stratification factor), advanced disease status determined by chest x-ray (stratification factor), Total CES Depression Scale Score, CD4 count among those HIV positive, viral load among those HIV positive
- Baseline TB diagnostic test results (AFB smear, drug susceptibility tests)
- Baseline lab results for AST, ALT, bilirubin, hemoglobin
- 2x2 table displaying concordance of site classification and central reader classification of advanced disease status by chest x-ray

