## 6.7 Secondary Outcome Measures

- Proportions in each arm, and difference in proportions with corresponding confidence interval for outcome measures 3.2.1A and B, 3.2.2, 3.2.5, 3.2.6, 3.2.9, 3.2.10.
- Contrasts that estimate the difference between mean change in QTcF scores between Arm 1 and Arm 2 from screening to weeks 2, 8, and 13 with corresponding 95% confidence intervals (outcome measure 3.2.3.1)
- Odds ratio and 95% confidence interval from proportional odds model for outcome measures 3.2.3.2 and 3.2.3.3. If proportional odds model does not hold, then difference in proportions for categories QTcF  $\geq 480$  ms and QTcF  $\geq 500$  ms between arms with corresponding 95% confidence intervals.
- Kaplan-Meier curves of time to culture conversion in liquid media, and solid media, censored at 26 weeks (outcome measure 3.2.4).
- Hazard ratio and 95% confidence intervals for time to culture conversion in liquid media, and solid media, censored at 65 weeks (outcome measure 3.2.4).
- Hazard ratio and 95% confidence intervals for time to positivity in liquid media at each time point. If proportional hazards does not hold, then we will report log-rank test. Side-by-side box plots of time to positivity (Days) at each time point (weeks 1, 2, 3, 4, 6, 8, 0, 12) (outcome measure 3.2.6)
- Estimates for changes in chest x-ray score in each arm from screening to EOT, and estimate of difference in change with 95% confidence interval (outcome measure 3.2.7)
- Contrasts that estimate the difference with corresponding 95% confidence interval between Arm 1 and Arm 2 for the change in total skin hyperpigmentation color difference from week 0 to each of weeks 8, 13, 26, and 65 at each of the following locations; (1) left cheek, (2) right cheek, (3) forehead, (4) chin, (5) using the location with the maximum change in total skin hyperpigmentation color difference. (outcome measure 3.2.12)
- Contrasts that estimate the difference in mean subjective 'change in coloration score' at each of weeks 0, 8, 13, 26, and 65 in Arm 1 vs Arm 2 with corresponding 95% confidence intervals (outcome measure 3.2.13)  
Contrasts that estimate the difference in mean subjective 'distress to skin coloration' score at each of weeks 0, 8, 13, 26, and 65 in Arm 1 vs Arm 2 with corresponding 95% confidence intervals (outcome measure 3.2.12)

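### The change-from-baseline analyses of chest X-ray score and mean QTcF leave out the baseline value, so their intervals are valid but wider than necessary

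*SAP*

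**What the plan says.** **CXR score (SAP 5.1.3.7).** Change from screening to end of treatment is compared between arms "using linear regression, with adjustment for stratification factors of HIV status and advanced disease status". Site and central readings are analysed separately, and the central reading takes precedence. Under SAP 3.2.7 the score is the percentage of lung affected, plus 40 if there is cavitation.

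**Mean QTcF (SAP 5.1.3.2).** Two models are planned. One compares mean change from screening "using a GEE model with exchangeable correlation structure and time by treatment interaction terms". The other is a linear mixed model of change from baseline: "Randomization arm and week (time) will be fixed effects and participant ID will be a random effect". Neither names baseline QTcF as a covariate or constrains the arms to share a baseline mean. Each visit's value averages the triplicate ECGs (SAP 3.2.3): "We will use the mean of all measurements (up to 3) that are readable and available".

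**Reporting (SAP 6.7).** The report will give contrasts for the difference in "mean change in QTcF scores between Arm 1 and Arm 2 from screening to weeks 2, 8, and 13", with 95% intervals, and for CXR an "estimate of difference in change with 95% confidence interval".

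Nothing else in the supplied documents adds a baseline term to either analysis.

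**The concern.** Analysing a change score without the baseline value fixes the regression slope of follow-up on baseline at 1. Where the true slope is below 1, which is usual for a repeated measurement, the change score carries extra variance, and part of any chance baseline difference stays in the arm comparison. Putting baseline in the model estimates the slope and removes that variance.

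For CXR, advanced disease (yes/no) does some of this work, but it is a two-level proxy for a score that can run from 0 to 100 + 40 = 140. SAP 6.2 also plans a "2x2 table displaying concordance of site classification and central reader classification of advanced disease status by chest x-ray". To the extent that the two readings disagree, the stratum may be a weaker proxy for the central-read score. The QTcF models have no proxy at all.

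What is at stake is the width of the reported intervals. Arm 2 was planned at about 55 participants and accrual closed early, so precision cannot be recovered by enrolling more.

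**Working it through.** **Inputs.** Planned sizes are 110 in Arm 1 and 55 in Arm 2 (SAP 2.4). The models are those above. The plan gives no SD, correlation, power or target width for either outcome, so there is no stated figure to reproduce. I assume:

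- rho, the baseline–follow-up correlation: 0.3, 0.5, 0.7 and 0.9;
- q, the share of baseline CXR variance explained by the strata: 25% and 50%;
- equal SD s at baseline and follow-up, relaxed at the end.

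**1. QTcF at one week, no other covariate.** Residual variance of the change is 2s²(1 − rho). With baseline in the model it is s²(1 − rho²). The ratio is (1 + rho)/2, and the width ratio is its square root. At rho 0.5: √(1.5/2) = 0.866.

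**2. QTcF mixed model.** Its arm term, with no week interaction, averages over visits (weeks 2, 8 and 13 assumed, with a common correlation). Variance of the mean change is s²[(1 + 2rho)/3 + 1 − 2rho] = (4/3)s²(1 − rho). Adjusted, it is s²[(1 + 2rho)/3 − rho²] = s²(1 − rho)(1 + 3rho)/3. The ratio is (1 + 3rho)/4. At rho 0.5: √(2.5/4) = 0.791.

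**3. CXR with the strata already in the model.** Suppose follow-up depends on the strata only through baseline. The change score's excess variance is then s²(1 − rho)²(1 − q), and the variance ratio is (1 + rho)/[(1 + rho) + (1 − rho)(1 − q)]. At rho 0.5 and q 0.25: √[1.5/(1.5 + 0.375)] = √0.80 = 0.894.

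Adjusted interval width as a fraction of planned width:

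| Analysis | rho 0.3 | 0.5 | 0.7 | 0.9 |
|---|---|---|---|---|
| QTcF, single week | 0.81 | 0.87 | 0.92 | 0.97 |
| QTcF, mixed model, average of three visits | 0.69 | 0.79 | 0.88 | 0.96 |
| CXR, q = 25% | 0.84 | 0.89 | 0.94 | 0.98 |
| CXR, q = 50% | 0.89 | 0.93 | 0.96 | 0.99 |

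One over the variance ratio, minus 1, gives the equivalent gain in sample size. For CXR this is 40%, 25%, 13% and 4% at q = 25%, and 27%, 17%, 9% and 3% at q = 50%.

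**Absolute example.** At 110 and 55, rho 0.5 and no other covariate, the factor is 2 × 1.96 × √(1/110 + 1/55) = 0.647. The 95% interval is 0.647 × √(2 × 0.5) = 0.65 SD wide as planned and 0.647 × √0.75 = 0.56 SD wide adjusted.

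**Chance imbalance.** A baseline imbalance of one standard error is s√(1/110 + 1/55) = 0.165 SD. The unadjusted estimate keeps a share (1 − rho) of it: 0.116, 0.083, 0.050 and 0.017 SD. For CXR the strata reduce this.

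**Unequal SDs.** In general the CXR excess is (s0 − rho·s1)²(1 − q), where s0 and s1 are the baseline and follow-up SDs; it is never negative. With s1 = 0.8·s0 and q from 0.30 to 0.64, the width ratio is 0.81–0.89 at rho 0.5 and 0.84–0.91 at rho 0.7. With s1 = 1.2·s0 and the same q, it is 0.95–0.97 at rho 0.5.

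**Simulation checks.**

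- Mean standard-error ratios (110 v 55, 4,000 runs per setting) were 0.847, 0.898, 0.942 and 0.984 for CXR at q = 25%, and 0.692, 0.793, 0.882 and 0.965 for the three-visit model. Both agree with the formulas.
- Coverage of the planned 95% intervals was 0.946–0.953 for CXR (99 v 50, 4,000 runs) and 0.937–0.957 for the QTcF GEE (110 v 55, 300 runs, simulation error about 1.3 percentage points). The planned intervals are therefore valid.
- Entering screening as a time level in the GEE, with no constraint, returned exactly the change-score result. That coding does not supply the adjustment.

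**The case against.** - **Nothing is invalid.** True. Both outcomes are secondary, tied to no decision rule, and QT risk is also described by the categorical measures. Chance imbalance is already allowed for in a valid interval, so it is the same precision loss seen another way, not a second harm.
- **The gain may be small.** This stands in part. The strata already absorb some of it for CXR, and averaging triplicate ECGs tends to raise rho for QTcF, which moves its gain toward the smaller end.
- **The largest figures match no listed interval.** SAP 6.7 lists week-specific QTcF contrasts, whereas the three-visit figures belong to the mixed model that 5.1.3.2 plans. The single-week row is the one to rely on for the reported contrasts.
- **The GEE description is not a full covariate list.** Coding detail sits in an Analysis Implementation Plan that was not supplied, so the SAP should say which coding is used. Either coding, without a baseline covariate or a constraint, gives the change-score result.
- **A common slope may not help under 2:1 allocation.** CXR end of treatment is week 13 in Arm 1 and week 26 in Arm 2, so slopes may differ by arm. In large samples the common-slope estimate is less precise than the change score only if one arm's slope exceeds 1. That is an edge case.
- **It is late.** SAP version 3.0 is dated October 2023, and screening and accrual had closed in April 2023. If nobody enrolled after that, the week-26 cut-off fell at about the SAP date. In an open-label trial, the date of any change therefore matters.

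**Conclusion.** The point holds as a precision improvement, not as the correction of an error. The planned intervals are valid. For rho 0.3 to 0.7 with equal SDs, baseline adjustment would narrow the week-specific QTcF intervals by 8 to 19%, and the CXR interval by 4 to 16% if the strata explain 25 to 50% of baseline variance. At rho 0.9 the gain falls to 1 to 3%. Rho, the SD ratio and the stratum share are all assumptions. The width ratios do not depend on the number enrolled, so early closure changes the absolute widths but not these percentages. No primary outcome or stated power figure is affected.

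**What to change.** **SAP 5.1.3.7:** add the baseline CXR score as a continuous covariate beside HIV status and advanced disease, taken from the same reader source (site or central) as the outcome.

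**SAP 5.1.3.2:** state how the GEE is coded.

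- Where change is the response (the mixed model, and the GEE if so coded), add baseline mean QTcF, with a baseline-by-week term in the GEE.
- If the GEE models QTcF values with screening as a time level, do not add baseline as a covariate; constrain the two arms to a common screening mean.

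If slopes are expected to differ by arm, a robust standard error or a centred baseline-by-arm term covers it.

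Make the change in a dated SAP revision before the analysis is run, and keep the unadjusted change as a supportive result. If the analysis has already been run, label the adjusted result as added afterwards.

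**Cost:** one degree of freedom in the CXR model and in the mixed model, and three in the GEE (baseline plus baseline-by-week over three weeks). No new data are needed. No participant is lost, because someone without a baseline value has no change score to analyse.

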#### **5.1.3.8 Proportion of participants who have a TB relapse (Objective 2.3.2.9; Outcome Measure 3.2.8)**

We will estimate the proportion of participants in Arm 1 and Arm 2 with TB relapse using Kaplan-Meier estimates and 95% confidence intervals at 6 months (Arm 1), 9 months (Arms 1 and 2), and 12 months post-treatment (Arm 1 only) in the start treatment/not late exclusion set. We define the time of relapse as the time from end of treatment until the first sputum sample that is culture

positive in liquid or solid media for an *Mtb* strain that has matching genotype with the baseline isolate. A second positive sputum sample obtained at least 4 hours following the first sputum collection is required to confirm a relapse. If the second sputum sample is negative, this will not be counted as a relapse. If a participant is lost to follow-up without a second sputum sample confirmation of relapse (including contaminated or missing), it will be counted as a relapse.

For monitoring and interim reviews, we will estimate the proportion of participants with a confirmed relapse over time with 95% pointwise confidence bands. In addition, we will estimate the proportion of participants with a suspected TB recurrence or poor treatment response after successful culture conversion, even if relapse/recurrence has yet to be confirmed bacteriologically.

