##### Unfavorable Outcome

- Absence of cure. A participant will be considered to have absence of bacteriological cure if a sputum sample obtained at or after end of treatment for Arm 1 (week 13), or at or after week 17 for Arm 2 is culture-positive in liquid or solid media for an *Mtb* strain genotypically matched with the initial isolate. A second sputum sample, obtained at least four hours following the first sputum collection (see section 6.2.3 of protocol), is required to confirm absence of bacteriological cure.
- Participants who die from any cause during study treatment or follow-up except from violent or accidental cause (e.g., road traffic accident).

- Participants who had a positive culture for *Mtb* when last seen, whether confirmed by a second sample or not, unless determined to have been re-infected.
- Participants experiencing extension of treatment beyond the nominal level (week 13 for Arm 1 and week 26 for Arm 2) due to clinically inadequate response. These cases should be managed individually in conjunction with and after having notified the A5362 Clinical Management Committee (CMC). Extension of treatment to make up missed doses will not count as unfavorable.

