#### 4.1.1 Analysis set definitions

##### 4.1.1.1 Analysis sets (used for primary (5.1.1) and key secondary (5.1.2) estimands):

- **Efficacy Set:**  
All participants who are randomized to study treatment and are not late exclusions.  
(Participants will be late exclusions if they do not have any positive culture (liquid or solid) at screening, entry, or week 1, or if they have TB that is RIF-resistant or INH-resistant identified at screening or entry.)
- **Safety Set:**  
All participants who start assigned study treatment.
- **Start treatment/not late exclusion set:**  
All participants who start assigned study treatment and are not late exclusions.
- **Alive/adequate treatment set:**  
All participants who complete an adequate course of treatment as defined within Sections 10.2.5 and 10.2.6 of the protocol and who do not die during treatment.
- **Per protocol Set:**  
All participants who start and complete assigned study treatment.

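### SAP 5.1.3.8 estimates relapse in a set, and with an event rule, that do not carry the end-of-treatment culture-conversion condition of outcome 3.2.9, and its heading cites the SAE outcome

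*SAP*

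**What the plan says.** **Outcome.** SAP 3.2.9 ties relapse to prior conversion: "For participants who had successful culture conversion through the end of study treatment, TB relapse is defined as a recurrence of TB" from the original strain, established by genotyping, between EOT and week 65.

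**Analysis set.** SAP 5.1.3.8 gives Kaplan-Meier estimates at 6, 9 and "12 months post-treatment (Arm 1 only) in the start treatment/not late exclusion set". Section 4.1.1.1 defines that set as "All participants who start assigned study treatment and are not late exclusions". Late exclusion depends on cultures up to week 1 and on resistance, not on culture status at EOT.

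**Event rule.** "We define the time of relapse as the time from end of treatment until the first sputum sample" that is positive with a genotype matching baseline. A second positive sample confirms it. Loss to follow-up without a second result still counts as relapse. Prior conversion is not mentioned here. It appears in 5.1.3.8 only for an additional monitoring estimate, of "suspected TB recurrence or poor treatment response after successful culture conversion".

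**Citation.** The heading reads "Proportion of participants who have a TB relapse (Objective 2.3.2.9; Outcome Measure 3.2.8". Outcome 3.2.8 is "Proportion of participants with one or more serious adverse events (SAEs) through week 65", and 5.1.3.5 uses that number correctly.

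**Related places.** Section 3.2.1 A counts as absence of cure a genotype-matched positive "obtained at or after end of treatment for Arm 1 (week 13"), or from week 17 in Arm 2. Section 5.1.3.9 carries the relapse approach over to recurrence, apart from the genotype match, while outcome 3.2.10 states no conversion condition. Section 6.7 lists 3.2.9 and 3.2.10 among the outcomes reported by arm and as a difference with a confidence interval.

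**The concern.** The outcome definition and the analysis section describe different quantities. Under 3.2.9 a participant who never converted by EOT cannot relapse, because the disease was not cleared. Under 5.1.3.8 the same participant is in the analysis set and, on the words of the event rule, can supply an event.

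LOA #1 gives treatment failure and recurrence together as the reason accrual was closed. A reader of the final report will want to know how much of the problem was failure to clear infection by EOT and how much was return of disease after apparent clearance. A relapse estimate that absorbs some failures, or that is diluted by people who cannot have the event, blurs that distinction. EOT is week 13 in Arm 1 and week 26 in Arm 2, so the share unconverted at EOT may differ by arm and the distortion need not cancel in the difference that 6.7 reports.

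**Working it through.** The plan states no relapse rate, power or precision for this outcome, so there is no figure to reproduce. The check is a comparison of the text, followed by an illustration.

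**1. The clock.** Week 65 - week 13 = 52 weeks, about 12 months (Arm 1). Week 65 - week 26 = 39 weeks, about 9 months (Arm 2). The latest time points in 5.1.3.8 therefore fit a clock that starts at nominal EOT. Someone who dies or is lost before EOT has no follow-up on that clock, although the named set includes them.

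**2. The condition.** It is present in 3.2.9. It is absent from the set definition in 4.1.1.1, from the 5.1.3.8 event rule and from the outcome cited in the heading. None of the five sets in 4.1.1.1 has a conversion condition, so choosing another set would not restore it.

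**3. What happens to a participant unconverted at EOT.**
- Excluded from the risk set: consistent with 3.2.9.
- Kept in the set with 3.2.9 applied to the event only: in the denominator but unable to have the event.
- 5.1.3.8 applied literally: a confirmed matched positive after EOT is a relapse, and also an absence of cure under 3.2.1 A.
- Censored at EOT: leaves the risk set at time zero, which has the same effect as exclusion.

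**4. Size, in one arm.** All inputs are assumptions, because the documents give none of them:
- f = share unconverted at EOT, 5-10%
- r = relapse risk among converters, 10-20%
- q = share of non-converters counted as relapses
- no censoring

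Estimate under 3.2.9 = r. Estimate in the unrestricted set = f × q + (1 - f) × r. Error = f × (q - r).

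| f | r | q = 0 (dilution only) | q = 0.5 | q = 1 (upper bound) |
|---|---|---|---|---|
| 5% | 10% | -0.5 | +2.0 | +4.5 |
| 5% | 20% | -1.0 | +1.5 | +4.0 |
| 10% | 10% | -1.0 | +4.0 | +9.0 |
| 10% | 20% | -2.0 | +3.0 | +8.0 |

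Errors are in percentage points. For example, at f = 10%, r = 10%, q = 0.5: 0.10 × (0.5 - 0.10) = +0.04. The error is zero if everyone in the set has converted at EOT, or if non-converters are censored there.

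**5. The between-arm difference.** This would need f, r and q separately for Arm 1 at week 13 and Arm 2 at week 26. None is available, so no figure is given.

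**The case against.** The strongest reply is that Section 3 defines outcomes and Section 5 analyses them. Relapse is a defined term in 3.2.9, and 5.1.3.8 then adds only its timing and confirmation. On that view the event inherits the conversion condition and the literal reading falls away. The heading also names relapse and Objective 2.3.2.9, the next section cites 3.2.10, and 6.7 lists 3.2.9 and 3.2.10 together, so the wrong digit would probably mislead few analysts. This is a fair reading of the event. It does not settle the risk set: non-converters would stay in a denominator in which they cannot have the event.

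A second reply is that relapse among all who started treatment and were not late exclusions is a coherent quantity and avoids a subset formed after randomisation. That is so, but the plan would then have to say that it is the intended quantity, and how non-converters and people who never reach EOT contribute to a clock that starts at EOT.

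Third, the Analysis Implementation Plan and the protocol body, which are not among the documents at hand, may hold a rule. The SAP sections would still disagree with each other.

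Fourth, the neighbouring items are small. Section 5.1.3.9 names genotype as the only exception, so its plain sense is that other conditions carry over; what remains is the silence of 3.2.10. Section 2.3 already limits non-primary objectives to estimates with confidence intervals.

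A reader might infer that the plan will report treatment failures as relapses and overstate relapse by up to 9 points. The documents do not support that. It requires setting 3.2.9 aside, every non-converter having a qualifying positive, and no censoring, on top of assumed values for f and r.

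**Conclusion.** The mismatch between 3.2.9 and 5.1.3.8 is real and should be corrected. The set lacks the conversion condition, the event rule does not repeat it, and the citation is wrong.

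On assumed inputs (5-10% unconverted at EOT, 10-20% relapse among converters), the single-arm error is about -0.5 to -2 points if non-converters only dilute the denominator and +1.5 to +4 points if half of them count as relapses. The range +4 to +9 points is a remote upper bound, and the error is zero if non-converters are censored at EOT. It would be tempting to conclude that the reported difference between arms is biased by a known amount or in a known direction; nothing in the documents allows that to be worked out.

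The scope is limited. Objective 2.3.2.9 is to estimate, no hypothesis test depends on it, and outcomes 3.2.1 A and B are unaffected.

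**What to change.** - In the 5.1.3.8 heading, cite 3.2.9 instead of 3.2.8.
- In 5.1.3.8, require culture conversion through EOT for a relapse event. Restrict the risk set at EOT to members of the named set who reach EOT in follow-up and are culture-converted. State which medium determines conversion: 3.2.4 treats liquid and solid separately, whereas the relapse event accepts either.
- Leave genotype-matched positivity without prior conversion to 3.2.1 A, where it already counts as absence of cure.
- In 5.1.3.9, say whether the restriction also applies to recurrence, since 3.2.10 states none. New-strain events cannot be left to 3.2.1 A, which treats them as unevaluable.
- In 6.7, label the between-arm difference for 3.2.9 as descriptive, and likewise for 3.2.10 if it is restricted.

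The cost is a risk-set and event sentence, a subset flag, a citation correction and a sentence in 5.1.3.9. The drawback is that the denominator is defined after randomisation, so the arms are no longer a randomised comparison for this outcome; 3.2.1 A and B keep that comparison. Dropping the condition from 3.2.9 instead would also make the sections agree, but it would leave failure and relapse merged.
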